4.1. General Considerations

Statistical analysis of this study will be the responsibility of Eli Lilly and Company (Lilly) or its designees. Any change to the data analysis methods described in the protocol will require an amendment ONLY if it changes a principal feature of the protocol. Any other changes to the data analysis methods described in the protocol, and the justification for making the change, will be described in this SAP or the clinical study report. Additional exploratory analyses of data will be conducted as deemed appropriate.

Unless otherwise stated, the efficacy analyses will be based on either efficacy analysis set 1 (EAS1, see the definition in Section 3) or efficacy analysis set 2 (EAS2, see the definition in Section 3). For treatment regimen estimand, EAS1 will be used. For efficacy estimand, other secondary and tertiary efficacy measures, EAS2 will be used (using the data up to the intercurrent events). The treatment comparison will be based on either 2-sided test or 95% CI.

Unless otherwise noted, the safety analyses will be conducted on the Safety Analysis set (SS, see the definition in Section 3). Percentages will be calculated using the mITT population as the denominator. For events that are sex-specific, the denominator and computation of the percentage will include only participants from the given sex.

For continuous measures, summary statistics will include sample size, mean, SD, median, minimum, and maximum for both the actual and the change from baseline measurements. For certain variables that are considered to be log-normally distributed, the geometric mean and coefficient of variation (CV) will be provided instead. Either the mixed model repeated measurement (MMRM) model or the analysis of covariance (ANCOVA) model will be used to analyze continuous outcomes. Least-squares (LS) means, and standard errors derived from the analysis models will also be displayed. Treatment comparisons will be displayed showing the treatment difference LS means and the 95% CIs for the treatment differences, along with the p-values for the treatment comparisons. For certain safety laboratory measures, log-transformed values will be analyzed in the statistical model instead. The actual, change from baseline and percentage change from baseline will be presented using the derivation based on the output from the statistical model and the assumption of lognormality.

estimand) first dose date of study treatment.	
Multiple imputation will be used to impute Multiple imputation approach will be us	sed
missing observations at baseline. to impute missing observations at these	•
sessions.	
CGM parameters The baseline will be derived from the data The CGM sessions prior to Weeks 4, 12	2
(efficacy estimand) collected during CGM session prior to the 26, 52, 78 (Visit 7, 15, 22, 30, 37) in EA	2, AS2
first dose date of study treatment.	152
Insulin dose during The baseline period is the lead-in period All scheduled visits between Week 0 the treatment period I prior to the initiation of study treatment (Visit 2) and Week 79 (Visit 27) in EAS	ດາ
The following variables will be derived.	.52
The following variables will be derived. The following variables will be derived.	1.
• daily dose in U	1.
• weekiy dose in U • uany dose in U	
• dose in U/kg/day • weekly dose in U	
I ne detailed description is added in • dose in U/kg/day	
Section 4.4.2.1. I ne detailed description is added in	

Analysis	Baseline Observations	Post-Baseline Observations
Fasting glucose by	The baseline period is the lead-in period	Data will be summarized for each visit as
SMBG	up to the first day of study treatment. The	an average of all Fasting SMBG from the
	average of all Fasting SMBG during Visit	time after the prior visit and up to that day
	2 date and on or prior to the first day of	of the visit.
	study treatment will be considered as	- For treatment regimen estimand,
	baseline.	measurements at Weeks 26, 52, 78 (Visits
	- For treatment regimen estimand,	22, 30, 37) in EAS1 for ANCOVA.
	multiple imputation will be used to impute	Multiple imputation approach will be used
	missing observations at baseline for	to impute missing observations at these
	treatment regimen estimand.	endpoint visits.
		- For efficacy estimand all
		available data after the day of first dose of
		study treatment up to Week 78 (Visit 37)
		in EAS2 for MMRM.
Fasting Serum	The baseline is the last non-missing	All planned measurements at scheduled
Glucose by central	assessment prior to or on the day of the	visits will be included.
lab	first dose of study treatment.	- For treatment regimen estimand,
	- For treatment regimen estimand,	measurements at Weeks 26, 52, 78 (Visits
	multiple imputation will be used to impute	22, 30, 37) in EAS1. Multiple imputation
	missing observations at baseline for	approach will be used to impute missing
	treatment regimen estimand.	observations at these endpoint visits.
		- For efficacy estimand all
		scheduled visits after the day of first dose
		up to Week 78 (Visit 37) in EAS2 for
		MMRM.
Participant-reported	The baseline period is the screening/lead-	• Treatment period starts on the first day
hypoglycemia	in period prior to the first day of study	of study treatment and ends on Week 78
	treatment.	(Visit 37), if study completed treatment
		or on the last dose date of study
		treatment $+$ 10 days and $+1$ day for
		LY3209590 and Insulin Degludec,
		respectively, if discontinued study
		treatment early.
		• Post-treatment period starts from end of
		Treatment period $+1$ day and ends on the
		last day in the study

Analysis	Baseline Observations	Post-Baseline Observations
TEAEs	The baseline period includes the	Safety analysis period starts after the first
	screening/lead-in period up to the first	dose(AE Start Relative to Exposure
	dose of study treatment (AE Start Relative	Assessment in CRF is used to determine)
	to Exposure Assessment in CRF is used to	and ends at the last visit in the study
	determine).	including safety follow-up period.
		Note: An AE will be TEAE if reported to
		be worsen in severity from baseline.
Safety laboratory	The baseline will be the last non-missing	All scheduled visits after the first day of
tests, vital signs and	assessment prior to or on the first day of	study treatment up to follow-up Visit 802
body weight	study treatment.	for MMRM and/or ANCOVA.
	Planned measurements at scheduled visits	Planned measurements at scheduled visits
	will be included.	will be included.
Elevated or low:	Starts from the screening visit and ends	Starts after the day of study treatment and
Laboratory values,	prior to or on the first day of study	ends at the last visit in the study including
vital signs, and body	treatment.	both treatment period and follow-up
weight categorical		period.
measures	All available scheduled and unscheduled	
	measurements will be included. The	All available scheduled and unscheduled
	baseline for weight will be the last non-	measurements in the specified analysis
	missing value during the baseline period.	period will be included.
Anti-LY3209590	Refer to PSAP.	Refer to PSAP.
antibody		
Patient-reported	The baseline will be the data collected at	• All scheduled visits after Week 0
outcomes	Week 0 (Visit 3).	(Visit 3).
		• Last collection after Week 0 (Visit 3).

Abbreviation: AE = adverse event; ANCOVA = analysis of covariance; CGM = continuous glucose monitoring; CRF = case report form; EAS1 = efficacy analysis set 1; EAS2 = efficacy analysis set 2; HbA1c = hemoglobin A1c; MMRM = mixed model repeated measurement; PSAP = program safety analysis plan; SMBG = selfmonitored blood glucose; TEAE = treatment-emergent adverse event.

All analyses will be implemented using SAS Enterprise Guide Version 7.1 or above.

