## Visit 5 (Week 2) - Visit 37 (Week 78)

Participants assigned to LY3209590 will administer their weekly doses during the remaining treatment period. Non-insulin antihyperglycemic medications will be continued after randomization. Study participants must measure their FBG levels each day when possible or at a minimum 3 times per week. The participant's FBG will be used to titrate basal insulin dose adjustments throughout the study based on the study titration algorithm (Section 6.1.3). Blinded CGM will be worn by participants at designated weeks (SoA Section 1.3, Section 8.1.5.2). Concomitant Meds, AEs, including hypoglycemia events, required questionnaires, diary compliance, and other study procedures will be recorded and completed as outlined in the SoA. The last dose of LY3209590 will be administered in the week prior to Visit 37 (Week 78), and the last dose of insulin degludec will be administered a day prior to Visit 37 (Week 78). Comprehensive efficacy and safety evaluations will be conducted through the end of the treatment period.

Randomly assigned participants who are discontinued from IP before the end of the treatment period at Visit 37 (Week 78) are encouraged to remain in the study for continued monitoring. Both efficacy and safety data will be collected as indicated in the SoA after the early discontinuation of IP.

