## 6.8.5. Treatment after the End of the Study

## 6.8.5.1. Treatment after Study Completion

Study interventions will not be made available to study participants after Visit 37 (Week 78) or after the participant's early discontinuation from study treatment.

At the last treatment visit (Visit 37 [Week 78] or ET visit), the investigator will prescribe a nonstudy basal insulin for use during the safety follow up period. Participants will continue their concomitant non-insulin antihyperglycemic medications at the discretion of the investigator and continue to monitor their FBG and complete the e-diary.

**Study Participants treated with LY3209590:** Study participants will receive the last injection of LY3209590 at Week 77 of the study and can begin the transition to the non-study insulin after Visit 37 (Week 78). At Visit 37 (Week 78), the investigator will review the instructions for transitioning to the non-study insulin. During this transition period, the participant's FBG should be used to guide dose initiation and adjustment for the insulin prescribed for the safety follow-up period.

No daily basal insulin will be required until the FBG is above 120 mg/dL (6.6 mmol/L) for 2 consecutive measurements. The prescribed non-study daily basal insulin should be started at a dose of 10 units/day and adjusted during the safety follow-up period based on FBG and according to the modified Riddle algorithm or investigator judgement in accordance with any country-specific label. Dose adjustments made for the non-study insulin during the safety follow-up period should be documented in the eCRF. An unscheduled visit in addition to Visit 801 may occur during this time to facilitate the transition to the non-study daily basal insulin.

Since LY3209590 has a half-life of approximately 17 days, a careful titration of the daily basal insulin is necessary to prevent hypoglycemia due to overlapping insulin action. Therefore, the investigator should consider titrating the daily insulin to reach 50% of the required daily dose at approximately 2-weeks and 80% at approximately 4-weeks.

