1.2. Study Design

- Study BDCU is a Phase 3, multicenter, randomized, open-label, comparator-controlled study to evaluate the efficacy and safety of once-weekly basal insulin (LY3209590) compared to insulin degludec in participants with T2D treated with basal insulin.
- The study includes a 3-week screening/lead-in period, a 78-week treatment period, and a 5-week safety follow-up period.
- Participants will continue prior stable diabetes therapy with 0 to 3 allowed non-insulin antihyperglycemic medications during the study.
- Participants will discontinue their previous basal insulin doses at randomization and will be assigned to either LY3209590 or insulin degludec U100.
- Assignment to treatment groups will be determined by an interactive web-response system (IWRS). Participants will be randomly assigned to 1 of the 2 treatment groups in 2:1 ratio (LY3209590 : insulin degludec) at Week 0 (Visit 3). Stratification will be by country, HbA1c stratum at Week -3 (Visit 1) (<8.0%, ≥8.0%), and the type of basal insulin regimen at randomization (a. typical once-daily basal insulin; b. U-300 or BID regimens).
- This is a treat-to-target study, both treatment groups will undergo titration to achieve an FBG target within the range of 80-120 mg/dL. The primary endpoint at Week 26 (Visit 22) is based on participants reaching stable insulin dose by 8 to 12 weeks and glycemic stability in advance of the 26-week primary endpoint Hemoglobin A1c measure.
- Rescue therapy will be considered during the treatment period if the participants meet the protocol criteria of severe, persistent hyperglycemia.
- If study intervention is permanently discontinued, the participant will be encouraged to continue participation in the study for continued monitoring. Both efficacy (including HbA1c) and safety data will continue to be collected per the schedule of activities in the protocol.

2. Statistical Hypotheses

Primary Hypothesis

The primary objective of this study is to test the hypothesis that LY3209590 is noninferior to insulin degludec on glycemic control as measured by change from baseline to Week 26 (Visit 22) in HbA1c in participants with T2D currently on basal insulin. Thus, the null hypothesis (H_{01}) to be tested is the difference in the change from baseline to Week 26 (Visit 22) in HbA1c (LY3209590 – insulin degludec) is greater than the noninferiority margin (NIM). The 2-sided 95% confidence interval (CI) will be used for testing the noninferiority.

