4.6.1. Extent of Exposure

Duration of exposure to study treatment will be summarized. No p-values will be reported in these tables as they are intended to describe the study populations, rather than test hypotheses about them.

Total patient-years of exposure will be reported. The number and proportion of participants falling into the following different exposure categories will also be summarized by study treatment:

- $>0, \ge 30$ days, ≥ 90 days, ≥ 180 days, ≥ 365 days, ≥ 545 days, and
- >0 and < 30 days, ≥30 and < 90 days, ≥90 and <180 days, ≥180 and < 365 days, ≥365 and <545 days, ≥545 days.

Exposure on study treatment will be calculated as:

- LY3209590: date of the last treatment administration date of first treatment administration + 7 days, and
- Insulin degludec: date of the last treatment administration date of first treatment administration + 1 day.

Total patient-years of exposure will be calculated by the sum of duration of exposure in days divided by 365.25. The following summary statistics will be provided: n, mean, standard deviation, median, minimum, maximum, interquartile range, and total exposure (that is, total patient-years).

All participants who complete the study treatment period are required to complete a safety follow-up period and participants who discontinue the study treatment prematurely are encouraged to remain in the study for safety monitoring. The duration on study from the first dose of study treatment to the study disposition (defined as treatment period disposition or follow up disposition, whichever is later)date will also be summarized by treatment.

A listing of exposure to study treatment and time in study since first dose will be provided.

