hypoglycemia events	0-78, 12-26, 26-52, 26-78, 52-	baseline HbA1c and baseline Level 1
(events/participant/year):	78 weeks, post-treatment period	hypoglycemia rate as covariates, log
All documented		(exposure/365.25 days) as the offset in the
		model.
Event rate of Level 2	Baseline, 0-6, 0-12, 0-26, 0-52,	Negative binomial regression with treatment,
hypoglycemia events	0-78, 12-26, 26-52, 26-78, 52-	baseline HbA1c and baseline Level 2
(events/participant/year):	78 weeks, post-treatment period	hypoglycemia rate as covariates, log
All documented		(exposure/365.25 days) as the offset in the
		model.
Event rate of Level 3	Baseline, 0-26, 0-52, 0-78, 26-	Negative binomial regression with treatment
hypoglycemia events	52, 26-78, 52-78 weeks, post-	and baseline HbA1c and baseline Level 3
(events/participant/100	treatment period	hypoglycemia rate as covariates, log
year):		(exposure/365.25 days) as the offset in the
All documented		model.
		If the number of events is too small to run the
		negative binomial regression, exposure
		adjusted rate calculated by total number of
		events divided by total exposure for individual
		patients will be provided and the empirical
		method (see Appendix 9 [Section 6.9] for
E (10/2		details) will be used for treatment comparison.
Event rate of Level 2/3	Baseline, 0-6, 0-12, 0-26, 0-52,	Negative binomial regression with treatment,
hypoglycemia events	0-78, 12-26, 26-52, 26-78, 52-	baseline HbA1c and baseline hypoglycemia
(events/participant/year):	78 weeks, post-treatment period	rate of the same hypoglycemia type as
All documented		offect in the model
Nocturnal		onset in the model.
• Non-nocturnal		The plots of the mean cumulative functions
		(MCFs) by each treatment arm will also be
		created The population mean for cumulative
		number of events up to time t $M(t)$ will be
		estimated using a nonparametric estimation
		method described by Nelson (2003).
Incidence of Level 1	Baseline, 0-6, 0-12, 0-26, 0-52,	Logistic regression with treatment, baseline
hypoglycemia events:	0-78, 12-26, 26-52, 26-78, 52-	HbA1c and baseline Level 1 hypoglycemia
All documented	78 weeks, post-treatment period	incidence as covariates.
Incidence of Level 2	Baseline, 0-6, 0-12, 0-26, 0-52,	Logistic regression with treatment, baseline
hypoglycemia events:	0-78, 12-26, 26-52, 26-78, 52-	HbA1c and baseline Level 2 hypoglycemia
All documented	78 weeks, post-treatment period	incidence as covariates.

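### The post-treatment hypoglycemia period has no fixed length, so one pooled comparison mixes about 5 weeks of transition in completers with up to about 1.6 years off study drug in early stoppers who stay

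*SAP*

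**What the plan says.** The participant-reported hypoglycemia row of the SAP 4.1 table ends the treatment period at Week 78 for those who complete treatment. For those who stop early it ends 10 days (LY3209590) or 1 day (degludec) after the last dose. It then adds: "Post-treatment period starts from end of" that period plus one day, with the end at the "last day in the study". No maximum length is given.

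The analysis table in SAP 4.6.3.1.1 lists this window among the periods to be compared ("78 weeks, post-treatment period") for Levels 1, 2, 3 and 2/3. Rates use negative binomial regression with an exposure offset. Incidence uses logistic regression with no exposure term. If Level 3 events are too few, the rate becomes total events over total exposure, compared by the empirical method of Appendix 9. SAP 4.1 allows the same fallback for hypoglycemia in general.

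The design has "a 78-week treatment period, and a 5-week safety follow-up period". On early stoppers, SAP 4.6.1 says that "participants who discontinue the study treatment prematurely are encouraged to remain in the study for safety monitoring", and Protocol 4.1.1 keeps collecting their safety data on schedule. Under Protocol 6.8.1, participants who need a non-study basal insulin as rescue stop study insulin but remain in the study.

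**The concern.** The pooled window holds two different situations. A completer is observed for about 5 weeks while moving from study insulin to another basal insulin. A retained early stopper is observed through that transition and then for months of ordinary non-study treatment.

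The first weeks carry a hazard that the protocol names. Because LY3209590 has a half-life of about 17 days, Protocol 6.8.5.1 says that "a careful titration of the daily basal insulin is necessary to prevent hypoglycemia due to overlapping insulin action". At 85 days after the last dose (5 half-lives) about 3% of the drug remains (0.5^5 = 0.031), so later time says almost nothing about that hazard.

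Two things are at stake. A short-lived excess after stopping one insulin could be averaged towards no difference. And the result would depend partly on how many early stoppers each arm keeps under observation, which in an open-label trial may differ by arm. No planned analysis of participant-reported events separates the two groups.

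**Working it through.** **Inputs.** SAP 5: 939 randomized 2:1 and 15% dropout at Week 26; nocturnal Level 2/3 rates of 0.67 and 1.1 per year, each with SD 2.6. SAP 1.2: 78 + 5 = 83 weeks. SAP 4.1: 10-day and 1-day tails. Not in the documents, so assumed: the fraction d stopping early, the fraction r of those who stay to Week 83, and the timing of stops. Stoppers who do not stay are given no post-treatment time.

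**1. The plan's own figure.** 626 × 0.85 = 532.1 and 313 × 0.85 = 266.05, which reproduces 532 + 266 = 798. The plan gives no figure for the post-treatment comparison.

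**2. Longest possible window.** 83 weeks is 581 days. After a single dose, LY3209590: 581 − 10 = 571 days = 81.6 weeks (1.56 years). Degludec: 581 − 1 = 580 days = 82.9 weeks (1.59 years). A completer has about 5 weeks.

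**3. Share of person-time.** Share = d·r·m / [d·r·m + (1 − d)·5], where m is the mean number of post-treatment weeks per retained stopper. With the LY3209590 tail (10 days = 1.4 weeks):
- stops uniform over Weeks 0-26: m = 83 − 13 − 1.4 = 68.6, or 13.7 times a completer
- stops uniform over Weeks 0-78: m = 83 − 39 − 1.4 = 42.6, or 8.5 times a completer

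Example (d = 15%, r = 50%, early stops): 0.15 × 0.5 × 68.6 = 5.145 against 0.85 × 5 = 4.25, so 5.145 / 9.395 = 55%.

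| d = 15% | r = 25% | r = 50% | r = 100% |
|---|---|---|---|
| Stops in Weeks 0-26 | 38% | 55% | 71% |
| Stops in Weeks 0-78 | 27% | 43% | 60% |
| Window capped at 5 weeks | 4.2% | 8.1% | 15.0% |

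Stoppers pass half when the fraction of randomized participants who stop and stay exceeds 0.85 × 5 / 68.6 = 6.2% (r of 41%) or 0.85 × 5 / 42.6 = 10.0% (r of 67%). With d = 5% the LY3209590 share never passes 42%.

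**4. Weight in the negative binomial model.** Dispersion k = (SD² − μ)/μ²: (6.76 − 0.67)/0.449 = 13.6 for LY3209590 and (6.76 − 1.1)/1.21 = 4.7 for degludec. A participant followed for t years carries weight μt/(1 + kμt). For 68.6 against 5 weeks the ratio is 1.98 (LY3209590) and 2.64 (degludec), or 3.48 with μ = 0.67 and k = 4.7. With d = 15%, the stoppers' share is 8-10% at r = 25% and 25-32% at r = 100%; with k = 4.7 in both arms it reaches 38% at r = 100%.

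**5. Incidence.** P(at least one event) = 1 − (1 + kμt)^(−1/k). With μ = 1.1 and k = 4.68, this is about 8% over 5 weeks and about 36% over 69 weeks, at an identical underlying rate.

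**6. Dilution under person-time weighting (illustrative).** Assume a rate ratio of 1.5 in the first 5 weeks and 1.0 afterwards, the same background rate throughout, d = 15% and early stops. At r = 50%, transition time is 0.85 × 5 + 0.075 × 5 = 4.625 and later time is 0.075 × 63.6 = 4.77, so the pooled ratio is (1.5 × 4.625 + 4.77)/9.395 = 1.25. At r = 25% and 100% it is 1.33 and 1.17.

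**The case against.** The strongest reply has four parts.

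- **Retention is unknown.** The 15% is a sample-size assumption that does not separate stopping treatment from leaving the study. Leavers add no time, and those taking the early-termination route (Protocol 4.1.1) may go straight to safety follow-up and add little. This stands. A reader might infer that early stoppers must dominate the person-time, but the documents support only that they can.
- **The rate model does not weight by person-time.** This also stands for the negative binomial analysis, where the shares in step 3 overstate the stoppers' influence. The rates used in step 4 are nocturnal, the only ones given. The reply does not cover the empirical fallback, which divides total events by total exposure, or the incidence models.
- **The period is nowhere assigned to washout.** That is correct. The purpose is inferred from Protocol 6.8.5.1, and an all-inclusive off-treatment period is consistent with the SAP's safety set. It is still hard to interpret when its length differs more than tenfold between participants.
- **CGM covers it.** SAP Appendix 6 plans a 4-week session after treatment, and SAP 4.6.3.1.2 analyzes it. This helps for CGM-detected Levels 1 and 2. It cannot supply Level 3 or participant-reported events.

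**Conclusion.** The point holds in a limited form. The window is open-ended, it is a planned between-arm comparison, and it pools about 5 weeks per completer with up to about 1.6 years per retained early stopper. Stoppers can make up much of the person-time, and most of it under plausible but unstated retention: above half once roughly 6-10% of randomized participants stop and stay, given 15% stopping.

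The effect differs by analysis. In the negative binomial rate it is moderate, about 8-38% of the weight at the SAP's nocturnal dispersion. It applies in full to the sparse-event fallback, which Level 3 is the likeliest to need. The incidence models compare very unequal observation times with no adjustment.

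A reader might infer that the nocturnal key secondary endpoint is affected as well. It is not: it stops at Week 78, and the primary and other key secondary endpoints do not use this window. This is an inexpensive improvement to a safety comparison that carries no multiplicity adjustment.

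**What to change.** In SAP 4.1 and 4.6.3.1.1, analyze post-treatment rate and incidence in one fixed window for every participant, starting the day after the treatment period ends, with exposure cut at the same day. About 5 weeks matches the safety follow-up, but a strict 35 days could remove scheduled follow-up. Visit 37 may fall 3 days early and Visit 802 may fall 7 days late, so the interval can reach 35 + 3 + 7 = 45 days. State an allowance that covers this. Report later off-treatment time in early stoppers separately, so that no event is lost. Alternatively, keep the period as defined and report completers (Study Period III) and early stoppers separately.

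The cost is SAP wording and one date derivation, with no new data. The main window will hold fewer events, so its interval will be wider.
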